## 1. ABBREVIATIONS

BBAQ – Barriers to Being Active Quiz  
 CMSA – Chedoke-McMaster Stroke Assessment  
 GAE – Group Aerobic Exercise  
 MOCA – Montreal Cognitive Assessment  
 NIH-SS – National Institutes of Health Stroke Scale  
 PASIPD – Physical Activity Scale for Individuals with Physical Disabilities  
 PROPEL – Promoting Optimal Physical Exercise for Life  
 SOEE – Short Self-Efficacy for Exercise scale  
 SSEE – Short Outcome Expectations for Exercise scale  
 SWT – Stepped Wedge Trial

## 2. INTRODUCTION

People often have low aerobic capacity after stroke, which makes even light physical activity effortful and can limit activities of daily living. Aerobic exercise is beneficial post-stroke for improving aerobic capacity, maintaining or promoting recovery and for general health, including reducing risk of another stroke or other cardiovascular events. Importantly, aerobic exercise is beneficial even early after stroke, and can be feasibly implemented during routine rehabilitation. However, length of stay in stroke rehabilitation is relatively short, so ongoing self-directed exercise post-discharge is necessary to maintain these benefits.

People with stroke do not maintain adequate levels of long-term exercise. Community-living people with stroke walk, on average, 70-5800 steps/day; less than the 6000 steps/day recommended for people with physical disabilities. Data from heart rate monitors reveal that, even when individuals with stroke are active, the activity is not of sufficient intensity. Chronic inactivity within this group means that any gains in aerobic fitness made during rehabilitation are quickly lost post-discharge. A vicious cycle can ensue: limited activity results in de-conditioning, functional decline and greater difficulty being active.

There is a need to establish strategies to promote long-term uptake of exercise after stroke. Most studies aiming to increase self-directed exercise post-stroke have been implemented in the community after formal rehabilitation is complete. While some community-based programs have reported increased physical activity after the program, many people have difficulty accessing community programs and consequently attendance can be low. The early recovery period during rehabilitation may be an optimal time to not only deliver fitness programming to increase exercise capacity, but also to shape long-term self-directed exercise behaviour. To our knowledge only one group has studied such a program during stroke rehabilitation. This study found that 67% of those who completed the intervention met exercise recommendations, compared to 55% in the control group. However, this study is limited by a non-randomized design, high rates of withdrawal in the intervention group compared to the control group (28% versus 12%), and low rates of compliance with the intervention (<67%). Furthermore, this study included individuals receiving rehabilitation for various conditions and was not focused solely on people with stroke, who have unique challenges to participating in exercise.

We developed Promoting Optimal Physical Exercise for Life (PROPEL) – an exercise and self-management program that aims to facilitate the transition to the community. Our pilot non-randomized study suggests that those who complete PROPEL are more physically active after discharge from rehabilitation than those who do not. The primary aim of this study is to *evaluate the effect of PROPEL delivered during stroke rehabilitation on participation in self-directed exercise after rehabilitation.* Our secondary aims are to evaluate the effect of PROPEL on self-efficacy and outcome expectations for exercise, and barriers to exercise. We hypothesize that, compared to those who

complete group aerobic exercise only, those who complete PROPEL will: 1) be more likely to meet the recommended intensity and duration of self-directed physical activity in the community (i.e.,  $\geq 150$ mins/week of moderate intensity exercise); and 2) report higher self-efficacy and outcome expectations for exercise, and fewer barriers to community activity.

### 3. METHODOLOGY

#### 3.1. Design overview

This study involves a single-blind, continuous recruitment short exposure, stepped-wedge cluster randomized controlled trial (SWT). Participants will be recruited from one of 6 sites in Ontario. Collectively, these 6 sites have approximately 710 admissions to out-patient stroke rehabilitation annually (St. John's – Sunnybrook: 150; Toronto Rehab – University Centre: 160; Toronto Rehab – Rumsey: 130; West Park: 150; St. Joseph's Care Group: 60; Hamilton Health Sciences: 60). At a randomly-determined time within the study period (see Figure 1), each site will transition from the control intervention (group aerobic exercise only; GAE) to the experimental intervention (PROPEL). New participants will be recruited continuously throughout the study period and will either complete the GAE or PROPEL intervention, depending on which program that site is administering at the time at which they are admitted to rehabilitation.

Each site will be staffed by a research assistant (RA) and a physiotherapist (PT). The RA will be responsible for recruiting participants and collecting data. The PT will administer the interventions.

	2017							2018							
	G1	G2	G3	G4	G5	G6	G7	G8	G9	G10	G11	G12	G13	G14	G15
Site A	1	1	1	1	1	1	1	1	1	1	1	1	1	1	1
Site B	0	0	0	1	1	1	1	1	1	1	1	1	1	1	1
Site C	0	0	0	0	0	0	1	1	1	1	1	1	1	1	1
Site D	0	0	0	0	0	0	0	0	0	1	1	1	1	1	1
Site E	0	0	0	0	0	0	0	0	0	0	0	0	1	1	1
Site F	0	0	0	0	0	0	0	0	0	0	0	0	0	0	0

**Figure 1: Intervention allocation schedule.** G1, G2 etc. are the 6-week long group aerobic exercise (GAE) or PROPEL groups. Each site should be able to complete 8 groups per year; however, only 7 groups will be completed in 2017 to allow for additional time at the start of the year to obtain research ethics approval, inter-institutional agreements, and pilot implementation at all sites (see also Figure 3). '0' indicates that the site will complete GAE in that time period, whereas '1' indicates that they will complete PROPEL. A simple randomization procedure will be used to determine the time at which each site transitions from GAE to PROPEL. Sites will be allocated in order by drawing names from a hat; e.g., the 1st site to be drawn will be Site A, the 2nd will be Site B, etc.

#### 3.2. Rationale for SWT design

The group format is essential to PROPEL (see below). We experienced from our pilot study that there was often a delay to start the group until there were  $\geq 3$  people referred. Therefore, a study design whereby individual participants are randomly allocated to either GAE or PROPEL would be problematic as there would be even greater delays in starting the groups. Likewise, a traditional cluster randomized controlled trial, where sites are randomly assigned to either complete GAE or PROPEL, would not be ideal due to the relatively low number of sites (6), and thus, reduced statistical power. Therefore, the SWT is a pragmatic trial design that is suitable for evaluating interventions that are implemented routinely at the level of cluster. It balances the need for robust evaluation with logistic constraints in program evaluation, particularly in cases of inter-site variability. Indeed, previous authors have argued that well-designed and executed SWTs can be as rigorous as traditional cluster randomized trials.

### 3.3. Interventions

The interventions will be implemented as part of routine care at all sites according to the schedule outlined in Figure 1 (e.g., Site B is expected to implement GAE in mid-February 2017, and PROPEL in around mid-May 2017). The interventions will supplement, rather than replace, current practice; that is, patients will still complete their regularly-scheduled physiotherapy, occupational therapy, and speech and language pathology sessions, as required. However, for patients who are enrolled in the GAE or PROPEL interventions, physiotherapists might choose to not complete individualized aerobic exercise during patients' regularly scheduled physiotherapy sessions as this will be completed as part of GAE/PROPEL, and to spend this time instead focusing on other rehabilitation goals (e.g., balance or gait retraining).

Both interventions involve supervised, individualized, group aerobic exercise up to 3 days/week for 6 weeks. Patients will be referred by their treating physiotherapist. The interventions will be implemented as part of routine care in out-patient rehabilitation at each site, and will be delivered in a 'closed group' format. That is, participants referred to the program will be placed on a waiting list until there are a sufficient number of participants to form a group ( $\geq 3$ ), and all participants in the group will start the program at the same time. This will ensure that the mean time post-stroke at study enrolment does not differ between the two phases of intervention. Prior to starting the group, participants may complete individualized or open-group aerobic exercise as part of their regular in- or out-patient rehabilitation.

#### 3.3.1. Control intervention – GAE

The control intervention will involve group aerobic exercise only (GAE). The intensity and duration of exercise within a session will be determined from a sub-maximal aerobic capacity test conducted prior to entry into the program using a protocol developed by our team. The choice of exercise modality for the submaximal test and for training (e.g., recumbent stepper, cycle ergometer, or treadmill) will be individually prescribed based on patients' sensori-motor recovery, postural control, functional abilities, and safety. Group exercise will be supervised by the PT. A typical exercise session will involve a 3-5 minute 'warm-up', 20-30 minutes of aerobic exercise at a target heart rate determined from the submaximal test, and a 3-5 minute 'cool-down' of low-intensity exercise, which we have shown to be feasible for this target population. Heart rate, blood pressure, rate of perceived exertion, workload, and duration of training will be documented for each session. These data will be reviewed by the PT with appropriate progression of the intensity and/or duration of exercise as necessary.

Patients in the GAE program may receive general advice to keep physically active after discharge, and may receive an individualized home exercise program, as is currently routine care at all sites.

#### 3.3.2. Experimental intervention – PROPEL

The PROPEL program, involves both group aerobic exercise and group discussion aimed at enabling participation in exercise after discharge. Components of the PROPEL program were developed according to the Transtheoretical Model of health behaviour change and Social Cognitive Theory. Participants will complete group exercise up to 3 days/week (described above for GAE). Participants will also attend 1-hour small group discussion sessions once weekly to learn self-management skills for exercise in preparation for discharge from rehabilitation. These group sessions include discussions to: identify and problem-solve around barriers to exercise; understand personal and general benefits of exercise; explore appropriate community resources for exercise; and find individualized and realistic strategies for incorporating exercise in a regular routine. The group format allows *vicarious experiences*; seeing others' achievements, especially for those uncertain of their own capabilities, may improve beliefs in the individuals' own capabilities. The group can also act as a motivator for

continued engagement in exercise to achieve personal goals, offering encouragement to attempt new exercises and challenge negative perceptions of ability (*social persuasions*). Exercise self-efficacy predicts exercise behaviour post-stroke, to facilitate self-efficacy for exercise, patients will learn how to monitor their own heart rate and rate of perceived exertion. Patients will also become comfortable with progressing their aerobic exercise and will set short- and long-term exercise goals. Access to a health care professional (PT) leading the group can increase an individual's belief about personal skill, and support in teaching stroke survivors how to exercise independently, promoting feelings of safety and confidence. Supportive planning and problem-solving to achieve long-term goals of continued exercise in the community would be fostered as patients transition from the fitness group to independent community programming or exercise.

### 3.4. Participants & recruiting

Individuals who complete either GAE or PROPEL as part of routine care at one of the 6 sites will be invited to participate in the study. To be eligible for referral to GAE or PROPEL, patients must be admitted to the facility for rehabilitation after a diagnosed stroke, and must be able to understand instructions. Patients will be excluded from GAE or PROPEL if they have conditions that limit their ability to exercise, including uncontrolled hypertension, uncontrolled diabetes, other cardiovascular morbidity that limits exercise tolerance (e.g., heart failure, abnormal blood pressure responses or ST-segment depression >2mm, symptomatic aortic stenosis, or complex arrhythmias), unstable angina, orthostatic blood pressure decrease of >20mmHg, or musculoskeletal impairments or pain. Additionally, participants will be withdrawn from GAE or PROPEL if significant cardiovascular abnormalities are observed during the sub-maximal exercise test. We have used these criteria to successfully enrol patients with stroke in aerobic exercise during in-patient rehabilitation with no serious adverse events. Referral to the group will be made by the patients' primary treating physiotherapists, who will document the patients' verbal consent for treatment, as is usual practice.

Participants will be considered for inclusion in the study if they are referred to the GAE or PROPEL program as part of their stroke rehabilitation. Participants will be excluded from the study if:

- They have a language or communication barrier that prevents completion of questionnaires (e.g., severe receptive or global aphasia or non-English speaking);
- They have cognitive impairment that would prevent participation in unsupervised exercise;
- They attend less than 50% of GAE/PROPEL sessions; and/or
- They attend less than 4 of the 6 group discussion sessions (for individuals referred to the PROPEL program).

Communication and cognitive capacity to participate in the study will be determined via consultation with participants' healthcare team.

Potential participants will be assessed for eligibility by the study PT within the final two weeks of the patients' participation in the GAE/PROPEL programs. The study PT, who is in the patients' circle of care, will ask eligible patients if they are interested in speaking with the RA about participating in the study. The RA will discuss the study at a time that is convenient for interested individuals. She will describe the study, as outlined in the consent form (Appendix A) and will answer any questions the patient may have about the study. The patient will be provided with a copy of the consent form and will be invited to discuss the study with friends or family members, and/or to take some time to think about being involved in the study. If a patient indicates that s/he would like to participate in the study, s/he will be asked to sign the consent form. At that time, the RA will arrange a time that is convenient for the participant to collect baseline data (see Section 3.6.3.). We will assume that patients who do not provide consent to the study within two weeks after they finish the GAE/PROPEL program are not interested in participating in the study.

In order to keep track of participants, we will request contact information of a friend or family member ('alternative contact'; Appendix B); this form will be completed by the alternative contact. Participants who provide consent for us to contact their friends or family members will be provided with this form at the time when written consent is obtained, and will be asked to return the form at the next visit or by mail (a stamped self-addressed envelope will be provided). This information will only be used to obtain information about the whereabouts of a research participant if we are unable to contact them after multiple attempts. Participants will primarily be contacted by telephone throughout the study, unless otherwise requested. Each time they are contacted, participants will be told when they should next expect to hear from the RA and will be asked to inform the RA of upcoming limited availability (e.g. due to vacation or scheduled surgery). A letter will be mailed to participants (Appendix L) who are unable to be reached: 1) because his/her telephone number is out of service; or 2) five attempts have been made to telephone the participant over the course of two weeks (with at least two voicemail messages for participants who have voicemail and have provided consent for us to leave voicemail). In the latter case, telephone calls will be placed at varying times of the day in an attempt to reach participants who are unavailable at the same time each day due to regular appointments. The letter will request that participants contact the RA. If the RA does not hear from the participant two weeks after the letter was mailed, the RA will contact the alternative contact.

In order to generate a CONSORT flow-diagram for participant recruiting, RA will count the number of individuals who are admitted to the out-patient stroke program and, of these, the number who are referred to the GAE or PROPEL program (Appendix C). The RA will also maintain documentation related to screening and enrolment of potential participants (Appendix D). Note that any identifying or health-related information will not be documented for individuals who do not consent to participate in the study.

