We will use the step activity, heart rate, and questionnaire data to determine if participants meet the recommended intensity and duration of physical activity in the community; that is, at least 150 minutes per week of moderate-vigorous intensity exercise. Participants will be deemed to meet the recommendations within a given week if they meet at least two of three criteria: 1) record at least 150 'active minutes' (from the step activity monitor); 2) record at least 150 minutes of heart rate between 55-80% of age-predicted maximum; and/or 3) report at least 150 minutes of moderate and/or vigorous intensity activity on the PASIPD.

**Figure 2: Hypothetical timeline for one participant.** The exact timing of in- and out-patient rehabilitation will vary for each participant. The sub-maximal aerobic capacity test is completed during in-patient rehabilitation. After this point the participant could participate in individual or open-group aerobic exercise during in- and out-patient rehabilitation (while waiting to be enrolled in the study intervention). The closed-group study intervention (group aerobic exercise (GAE) only or PROPEL) will likely start during out-patient rehabilitation, though some patients may start during in-patient rehabilitation. The participant will be enrolled in the study at the end of the study intervention, at which point cohort descriptors, the Short Self-Efficacy for Exercise (SSEE) scale, and the Short Outcome Expectations for Exercise (SOEE) scale will be collected. Activity monitoring will be conducted for 7 days continuously at three time points: 1) one month; 2) 4 months; 3) and 6 months after the end of the study intervention. The Barriers to Being Active Quiz (BBAQ) will be conducted at the 1-month post-intervention time point.

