### 3.6.3. Cohort descriptors

The following information will be obtained from chart review in order to characterize individuals who participate in the study: age, sex, time post-stroke (at enrolment into the study), lesion location, and medical conditions/history (Appendix F). The National Institutes of Health Stroke Scale (NIH-SS), the Chedoke-McMaster Stroke Assessment (CMSA) foot and leg scores, and the Montreal Cognitive Assessment will be administered at enrolment into the study by the RA or study PT; however, if these measures were conducted as part of clinical care within 1-week of study enrolment, the scores will be extracted from the hospital charts to minimize participant burden. The NIH-SS is an 11-item scale that provides a gross measure of the effects and severity of stroke. The NIH-SS has good intra-rater (ICCs=0.93) and inter-rater (ICCs=0.95) reliability. The CMSA assigns a score according to the level of motor recovery in the foot and leg and is frequently used to evaluate level of motor recovery post-stroke in clinical settings. The CMSA foot and leg scores have good intra-rater (ICCs=0.94-0.98) and inter-rater (ICCs=0.85-0.96) reliability. The MOCA is a paper-based test that can be used to screen for mild cognitive impairment; patients are scored on visuospatial and executive function, naming, memory, attention, language, abstraction, delayed recall, and orientation.

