### 3.8. Statistical analysis

We will compare cohort descriptors between the two phases (GAE and PROPEL) using t-tests, Mann-Whitney *U* tests, or chi-square tests, as appropriate. If phases significantly differ at baseline on cohort descriptors these measures may be used as covariates in the analysis. To test our primary hypothesis, we will compare the proportion of active and inactive individuals at the final assessment point (6 months post-intervention) using mixed-model logistic regression, with fixed effects of time and phase and random effect of cluster (site). We will also examine between-phase differences in physical activity at the 1-month and 4-month time points, which could reveal short-term benefits of PROPEL, even if there are no differences at 6-months. A similar mixed-model ANOVA will be used to compare SSEE, SOEE, and BBAQ scores between programs to test the secondary hypothesis.

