Participants with heart rate/blood pressure measurements outside the acceptable range will also be questioned regarding recent medications (what they have taken and when, or if they have not taken their usual medications), when they last had something to eat and drink, and if they recently took caffeine or exercised. The decision to continue or terminate the session will be made by the PT considering factors such as the participants' usual resting heart rate/blood pressure, how far the measured values are outside of the acceptable range, the participants' usual medications (e.g., beta-blockers), and the participants' perception of how they are feeling. If the session is terminated, the PT may consult with the patients' physiatrist or other physician.

The Canadian Stroke Best Practice Recommendations also recommend including a plan to enable patients to continue to exercise post-discharge, including addressing barriers to physical activity. However, the specific education, self-management, and problem-solving components of the PROPEL program are not part of routine care at all sites. The additional risk to participants in completing this component of the PROPEL program is minimal. Participants can opt out of any part of the discussion if they feel uncomfortable.

The additional measures conducted as part of the study pose minimal risk to participants. The CMSA, NIH-SS, and MOCA are frequently conducted as part of clinical care in stroke rehabilitation. Other measures are questionnaires which ask routine questions about physical activity behaviour and lifestyle. Despite the minimal risk involved in these measures, participants will be reminded that they can opt out of any testing and/or decline to answer any of the questions in the questionnaires. The activity monitoring also poses minimal risk to participants; the devices are available commercially and are worn daily by millions of individuals around the world. Participants may develop skin irritation from wearing the device daily; they will be instructed to remove the device if this occurs. Participants may feel burdened by donning and doffing the activity monitors each day.

The study PT will document any adverse events that occur during the interventions; the RA will document adverse events for participants who enrol in the study during the follow-up period (Appendix I).

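### NIH-SS, CMSA foot/leg and MoCA are scored at or near the end of the 6-week program, but Section 3.8 tests them as baseline and allows them as covariates in the primary model

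*Combined protocol and SAP*

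**What the plan says.** Eligibility is assessed "within the final two weeks of the patients' participation in the GAE/PROPEL programs" (Section 3.4). Consent stays open for a limited time after that: the plan assumes that "patients who do not provide consent to the study within two weeks after they finish the GAE/PROPEL program are not interested". When the form is signed, "the RA will arrange a time that is convenient for the participant to collect baseline data".

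The Figure 2 caption in Section 3.6.1 confirms the order: "The participant will be enrolled in the study at the end of the study intervention, at which point cohort descriptors" and two exercise-belief scales are collected.

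Section 3.6.3 says that the NIH-SS, the CMSA foot and leg scores and the MoCA "will be administered at enrolment into the study by the RA or study PT". A chart score may replace the test only if it was obtained within one week of enrolment.

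Section 3.8 compares the cohort descriptors between the GAE and PROPEL phases and continues: "If phases significantly differ at baseline on cohort descriptors these measures may be used as covariates in the analysis". That sentence makes no distinction between descriptors fixed before the program and descriptors measured at its end.

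**The concern.** A baseline covariate should be fixed before the treatment can act on it. These three scores are taken after most or all of the allocated program, in patients who have already met the attendance rule and agreed to take part. Two problems follow.

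- **Comparability.** A phase difference in stroke severity, leg recovery or cognition could reflect who was referred, who completed and consented, or what the program did. The planned data cannot separate these. An entry difference could also be blurred by six weeks of rehabilitation.
- **Adjustment.** If PROPEL moves one of these scores more than GAE does, and the score is related to being active at 6 months, conditioning on it removes part of PROPEL's own effect. The rule in Section 3.8 is triggered by a phase difference, so adjustment becomes more likely when such a shift has occurred.

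With only six sites randomised, chance differences between phases are plausible, so a sound comparability check has value here.

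**Working it through.** **Timing** (Sections 3.3, 3.4, 3.6.3), counted in weeks from the first session of a 6-week program:

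- Earliest eligibility assessment and consent: 6 − 2 = week 4.
- Latest consent: 6 + 2 = week 8. Data collection is arranged from then.
- Earliest admissible chart score: 4 − 1 = week 3.

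No route in the plan reaches week 0. For these three measures, every planned value post-dates program start.

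**The planned effect** (Section 3.9: 25% vs 50% active, ICC 0.05, 6 sites, 96 per phase, 80% power, alpha 0.05, taken as two-sided). Unpooled two-proportion formula:

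- n = (1.960 + 0.842)² × (0.25 × 0.75 + 0.50 × 0.50) / 0.25² = 7.849 × 0.4375 / 0.0625 = 54.9.
- With 96 / 6 = 16 per site, the design effect is 1 + 15 × 0.05 = 1.75.
- 54.9 × 1.75 = 96.1, which matches 96. Dividing by 0.80 for drop-out gives 120, which also matches.

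The timing point does not depend on this figure. It supplies the 25-point difference used next.

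**Illustrative loss from adjustment.** The documents give no program effect on these scores and no correlation with activity, so every input here is an assumption.

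- Let S be the enrolment score in SD units, with mean 0 in GAE and d in PROPEL.
- Let logit P(active) = a + b·S + c·phase, with a and c set so that 25% of GAE and 50% of PROPEL are active overall.
- The adjusted difference is the average over the pooled distribution of S of P(active | S, PROPEL) − P(active | S, GAE), found by numerical integration.

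| Shift d (SD) | OR 1.5 per SD | OR 2.0 per SD | OR 2.5 per SD |
|---|---|---|---|
| 0 | 25.0 | 25.0 | 25.0 |
| 0.1 | 24.1 | 23.6 | 23.3 |
| 0.2 | 23.3 | 22.2 | 21.5 |
| 0.3 | 22.4 | 20.8 | 19.7 |

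The loss runs from 0 to 25 − 19.7 = 5.3 points. It is zero along the whole row where PROPEL shifts the score no more than GAE.

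**How often the rule would fire.** For a two-sample t-test with 120 per phase, two-sided 5% and clustering ignored, the non-centrality is d × √(120/2). The chance of a significant difference is 12% at 0.1 SD, 34% at 0.2 SD and 64% at 0.3 SD. If adjustment follows only a significant test, and allowing for the larger observed shift when it does, the average loss in the middle case (0.2 SD, OR 2) falls from 2.8 points to about 1.6. In the worst case it falls from 5.3 to a little over 4.

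**Blurring of an entry difference.** If the phases truly differed by 0.3 SD at entry, with no further program effect and pre-post correlation r, the enrolment scores would differ by 0.3 × r: 0.24 SD at r = 0.8 and 0.18 SD at r = 0.6. On the same t-test, the chance of detection falls from 64% to 46% and 28%. The values of r are assumed.

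**The case against.** The strongest reply is that harm from adjustment needs a differential shift. Both phases receive the same supervised exercise, and PROPEL adds a weekly discussion hour on barriers, resources and goals. Nothing in the plan claims that this changes stroke severity, leg recovery or cognition. Section 3.8 also says only that covariates may be used, and only after a significant difference. This stands, and it is why the loss cannot be put above zero with confidence.

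Three stronger readings are tempting, and the documents do not support them:

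- *That the trial has nothing with which to show comparability.* Age, sex, lesion location and medical history come from chart review (Section 3.6.3), and pre-stroke activity comes from the Schmidt scale. The program cannot have changed these. The gap concerns three instruments.
- *That the primary analysis will adjust for post-treatment values, at a loss of 3 to 21% of the effect.* Adjustment is permitted, not planned, and that range assumes a non-zero shift and certain adjustment.
- *That the exercise test given before the program already fills the gap.* Section 3.3.1 does describe "a sub-maximal aerobic capacity test conducted prior to entry into the program", but its modality is chosen patient by patient. The Figure 2 timeline places it in in-patient rehabilitation, with other aerobic exercise possible afterwards. It is a weak common covariate and does not replace the three scores.

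It can also be said that baseline here means the start of follow-up. As a description of the patients that is reasonable. It does not cover using the same values to check comparability or to adjust the treatment effect.

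Finally, late scores may carry information about selection by attendance and consent that earlier scores miss. That is fair. Earlier measurement does not remove that selection, which is a separate matter.

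**Conclusion.** The point holds for the NIH-SS, CMSA foot and leg, and MoCA. All planned values fall after the program has begun, at or near its end, while Section 3.8 handles them as baseline and leaves them open as covariates in the primary model. Comparability of the phases at entry on these three measures cannot be shown, whether or not anyone adjusts.

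The effect on the primary estimate is unknown and may be nil. A range of 0 to about 5 of 25 points rests on an assumed differential shift of 0 to 0.3 SD, an assumed odds ratio of 1.5 to 2.5 per SD, and adjustment being carried out. It is zero if PROPEL does not shift these scores more than GAE. This is a worthwhile and inexpensive improvement to the plan, not a flaw that invalidates the trial.

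**What to change.** - **Section 3.8.** Limit both the between-phase comparability test and the primary-model covariates to values the program cannot have changed: age, sex, lesion location, medical history, pre-morbid activity, and clinical scores recorded before the program.
- **Section 3.6.3 and Appendix F.** Add extraction of the last NIH-SS, CMSA foot and leg, and MoCA in the chart before the first GAE or PROPEL session, where available. Section 5.1 gives reason to expect that many charts will have them: "The CMSA, NIH-SS, and MOCA are frequently conducted as part of clinical care in stroke rehabilitation".
- **Enrolment scores.** Keep the existing one-week chart rule for these, so that no testing is added. Label them end-of-program descriptors and do not use them as covariates in the primary model.

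The cost is a change of wording and a few fields in a chart review that is already planned, with no new visit or test. Some charts will lack a pre-program score or have it at varying dates, and the documents give no estimate of how many, so the plan must say how missing values are handled. The change does not remove selection by attendance and consent.
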